## 5.0 RANDOMIZATION PROCEDURES

Patients will be randomized to the two arms using permuted block randomization (e.g. blocks of variable sizes 4 or 6) stratified by HIV status. The randomization will be done by a statistician and the randomization codes will not be available to study staff until the participant is randomized. This will be done by providing sealed opaque randomization envelopes to the research staff at the CAPRISA – eThekweni CRS. The envelopes will be stored in a locked cupboard and opened in sequential order by study team members authorized to perform randomization procedures by the Principal Investigator. After opening the envelopes, staff will record the date and time of opening the envelope and their staff details. The patient’s allocated arm will then be recorded on a randomization log.

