## SCHEMA

**Design:** This is an open label randomized controlled clinical trial comparing two regimens for treatment of smear-positive pulmonary TB, among patients previously treated for TB. The primary objective is to determine if a Moxifloxacin-containing regimen, substituting Moxifloxacin for Ethambutol, of 24 weeks duration is superior to a control regimen of 24 weeks duration in improving treatment outcomes in patients with recurrent TB.

**Duration :** Intervention Arm : Approximately 6 months treatment + 12 months post treatment follow up

Control Arm : Approximately 6 months treatment + 12 months post treatment follow up

**Sample Size:** 330

**Population :** This study will include adults 18 years and over with a previous history of TB. HIV infected and uninfected patients will be included in the study as well as patients on ARVs provided that these are not contra-indicated with any of the study drugs. Patients with *M tuberculosis* resistance to Rifampicin will be excluded at screening using Gene Xpert technology.

**Randomization:** Patients will be randomized to receive 1 of 2 TB retreatment regimens

[figure not shown]

Figure 1 : IMPRESS patient screening and randomization arms

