### 3.0 STUDY DESIGN AND SETTING

This is an open label randomized controlled clinical trial comparing two regimens for treatment of smear-positive pulmonary TB, among patients previously treated for TB. Patients will be randomized to receive one of the two TB retreatment regimens as listed below. In the Intervention Arm, Moxifloxacin will be substituted for Ethambutol. “Study drugs” refer to all the drugs listed in Table 1.

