### 3.1 Study setting: study site and populations

The study will be conducted at the CAPRISA eThekweni Clinical Research Site (eCRS), adjoining the largest government outpatient TB facilities, the Prince Cyril Zulu Communicable Disease Centre (PCZCDC). The PCZCDC provides free diagnosis and treatment for patients with TB in Durban. The clinic is readily accessible by public transport. Over the last 3 years, TB cases in the Durban region have increased by 38%. In 2001, 7,819 received TB care, 70% had pulmonary tuberculosis. In 2008, 4179 TB patients were managed at the clinic and of these, 2204 had smear positive TB. Approximately 35% of patients have a past history of TB. The majority (91%) of TB patients are black Africans, unemployed (53%), women (39%), 69% are HIV co-infected and the median age was 33 years (range: 5-72 years). The change in number from 2001 to 2008 is due to the decentralization of TB services. In order to make treatment even more accessible and also improve case holding. Laboratory support is available onsite.

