## 2. STUDY DESIGN

This is an open label randomized controlled clinical trial comparing two regimens for treatment of smear-positive pulmonary TB, among patients previously treated for TB. The primary objective is to determine if a Moxifloxacin-containing regimen, substituting Moxifloxacin for Ethambutol, of 24 weeks duration is superior to a control regimen of 24 weeks duration in improving treatment outcomes in patients with recurrent TB.

This study will include adults 18 years and over with a previous history of TB. HIV infected and uninfected patients will be included in the study as well as patients on ARVs provided that these are not contra-indicated with any of the study drugs. Patients with M tuberculosis

resistance to Rifampicin will be excluded at screening using Gene Xpert technology. A maximum of 330 participants will be included in the study.

Patients will be randomized in a 1:1 ratio to receive one of the two TB retreatment regimens, as outlined in the table below.

|                         | Intensive Phase (2 months) | Continuation Phase |
|-------------------------|-----------------------------------|---------------------------|
| Intervention Arm | HRZM* daily (2 months)            | HRM* daily (4 months)     |
| Control Arm      | HRZE* daily (2 months)            | HR* daily (4 months)      |

\* Isoniazid (H), Rifampicin (R), Pyrazinamide (Z), Moxifloxacin (M), Ethambutol (E)

The duration of TB treatment may increase due to a delay in the time to sputum conversion which will result in the extension of TB treatment beyond 6 months. Following treatment, participants will be followed up on a two-monthly basis for 12 months.

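### Protocol 5.0 prints example block sizes for an open-label, single-site trial; this makes some upcoming assignments predictable with high confidence, and removing them costs nothing

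*Protocol*

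**What the plan says.** - **Scheme.** Protocol 5.0 specifies "permuted block randomization (e.g. blocks of variable sizes 4 or 6) stratified by HIV status". The sizes are introduced as examples; neither document states the sizes actually used or their mix. SAP section 2 adds: "Patients will be randomized in a 1:1 ratio to receive one of the two TB retreatment regimens".
- **Concealment.** Protocol 5.0 has a statistician prepare the list and keeps codes from study staff until the patient is randomized. It does this by "providing sealed opaque randomization envelopes to the research staff at the CAPRISA" site. Envelopes are kept in a locked cupboard and "opened in sequential order by study team members authorized to perform randomization procedures by the Principal Investigator". Staff record the date, time and their own details, and enter the arm on a randomization log.
- **Visibility.** Protocol 3.0: "This is an open label randomized controlled clinical trial comparing two regimens for treatment of smear-positive pulmonary TB". Protocol 3.1 names one research site, although section 10.1 draws patients from several facilities and has clinicians and nurses there trained on the protocol.
- **Order of events.** Protocol 7.2.2 requires the HIV result before randomization and has a study clinician assess eligibility first. The note under section 4.2 gives eligibility to the site investigator or a designate.
- **Not stated.** Neither document restricts who may know the block sizes, uses central allocation, or requires the person opening the envelope to differ from the person who judged eligibility.

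**The concern.** A sealed envelope protects the next assignment only as far as it cannot be inferred from earlier ones. Here the arm of each enrolled patient is known, there are two sequences to follow, and the stratum of the next patient is known before the envelope is opened. Printing the candidate block sizes also tells an observer when a block must be close to completion.

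A confident prediction could influence whether a patient is entered now, deferred within the 14-day screening window, or judged just inside or outside a criterion such as the Karnofsky threshold. The resulting imbalance would be in who enters each arm. A culture-based endpoint limits biased assessment but not that. The SAP does not address it either: section 6.3 names no covariates for its regression model and plans no check for selective enrolment.

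**Working it through.** **Inputs.** 1:1 allocation (SAP 2); blocks of 4 or 6, two HIV strata (Protocol 5.0); 330 patients (Protocol 9.1); 69% HIV co-infected at the clinic (Protocol 3.1), so 0.69 × 330 ≈ 228 and 102 per stratum. Assumptions: the two sizes are equally likely, and the guesser knows every earlier allocation in the stratum.

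**Plan's own figures.** The documents give no predictability figure to reproduce. The 330 does reproduce (165 per arm for 75% versus 60%, two-sided 0.05, continuity-corrected; power 80.0%) and is unaffected by this point.

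**Step 1: average guess rate.** The guesser picks the arm that is behind in the stratum and tosses a coin when the arms are level. Expected correct guesses in a block of size b:

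b/2 + (2^b / C(b, b/2) − 1) / 2

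- b = 4: 2 + (16/6 − 1)/2 = 2.833, or 70.8%
- b = 6: 3 + (64/20 − 1)/2 = 4.100, or 68.3%
- Equal mix: (2.833 + 4.100)/10 = 69.3%
- 25% of blocks of size 4: (0.25 × 2.833 + 0.75 × 4.100)/5.5 = 68.8%
- 75% of blocks of size 4: (0.75 × 2.833 + 0.25 × 4.100)/4.5 = 70.0%

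This strategy does not use the block sizes. A simulated optimal guesser who knows that the sizes are 4 or 6 also scores 69%, so knowing the sizes does not raise the average. Someone who ignores the HIV strata reaches about 64%. (The match between 69% guessed and 69% HIV co-infected is coincidence.)

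**Step 2: confidence of the guess.** The optimal guesser was simulated over sequences of 228 and 102. At each patient the probability of each arm was updated from the history.

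| True blocks | What the guesser considers | Correct | Called at ≥80% | Certain |
|---|---|---|---|---|
| 4, 6 | 4 or 6 | 69% | 26–27% | 5–6% |
| 4, 6 | 4 to 10 | 69% | 5–6% | 0% |
| 4, 6 | 2 to 10 | 69% | about 6% | 0% |
| 6, 8, 10 | 6, 8 or 10 | 66% | 15% | 1.5% |

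Rows 2 and 3 assume that the guesser weights the even sizes in the range equally at each new block and does not learn the sizes from the accumulating sequence. A patient observer could narrow the gap.

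**Step 3: an alternative list.** A big-stick design (coin toss unless the stratum imbalance reaches 4) gives 56% correct on average but about 12% certain assignments, roughly twice the figure in row 1.

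**The case against.** The strongest reply is that this is a common and reasonably protected design: a list prepared by a statistician, variable blocks, opaque envelopes, locked storage, sequential opening and a dated record. Eligibility already precedes randomization. Most entry criteria are objective (smear, GeneXpert, laboratory limits), which leaves little room to act on a guess. The sizes are only examples, and a guess rate is not a bias.

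Much of this stands. The safeguards are real against early opening, though not against inference from past allocations. The limited discretion at entry is a good reason to rate the point low.

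Three stronger readings are tempting and are not supported:

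- **That printing the sizes causes the 69%.** It does not; the lagging-arm strategy reaches it without them. Deleting the phrase would leave that figure unchanged.
- **That the same people recruit, judge eligibility and open envelopes.** The documents give eligibility to an investigator, designate or study clinician, recruitment to recruiters and referring facility staff, and opening to authorized team members. They do not say these are the same people; they only fail to require that they differ.
- **That allocation was subverted or the comparison is biased.** Nothing in either document shows this.

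**Conclusion.** The point holds as a modest weakness in concealment. If blocks of 4 and 6 are used in equal mix, the ceiling on correct guesses is about 69% (68.3% to 70.8% across every possible mix). This results from small blocks, open-label treatment, one site and one two-level stratification factor. The separable cost of printing the sizes is in the confident calls: about 26% of assignments predictable at 80% or more and about 5% certain, against roughly 5–6% and none when the sizes are unknown.

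These figures depend on complete tracking within stratum, on the example sizes being those used, and on the assumed range of sizes that an uninformed guesser entertains. They measure opportunity, not bias. The change is worth making because it is nearly free, not because the trial is unsound without it.

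**What to change.** 1. Delete the parenthetical block sizes from Protocol 5.0 and record them in a document restricted to the randomization statistician. Cost: one phrase.
2. Add to section 5.0 that the envelope is opened by an authorized team member other than the clinician who signed off eligibility. Sections 4.2 and 7.2.2 already put eligibility first; only the different-person requirement is new. Existing staff can do this, at the cost of having a second person available.
3. If envelopes remain to be generated, wider undisclosed blocks are an option. Even if known, sizes 6, 8 and 10 give 66% correct, 15% called at 80% or more and 1.5% certain. The gain in the average is small, and the price is somewhat looser balance within each stratum. A big-stick list is not recommended without stating its trade-off: 56% correct on average, but about 12% certain.
4. The documents do not give enrolment status, and the SAP's change log carries 2017 and 2018 versions under a heading that refers to the period after trial initiation. If the list is already used up, report the block sizes used and who opened the envelopes, and check whether baseline prognostic factors track the predicted allocation. This needs only data already held.

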## 6.0 STUDY TREATMENT

### 6.1 Regimens, Administration and Duration

Once randomized to either the Control or Intervention arms the study drug is to be self-administered once daily before meals. Treatment should be commenced no more than 3 days after randomization. The Control and Intervention arms will follow the South African National Tuberculosis dosing guidelines for re-treatment cases as closely as possible. All patients will receive pyridoxine 50mg daily whilst in the study.

**Table 2: Study drug regimens and duration: Control arm**

Pre-treatment body weight  (kg)	Intensive phase 7 days a week for 8 weeks  (56 doses)	Continuation phase – 7 days a week for 16 weeks  (112doses)	
	RHZE (150,75,400,275 mg)	RH (150,75 mg)	RH (300,150mg)
30-37	2 tabs	2 tabs	
38-54	3 tabs	3 tabs	
55-70	4 tabs		2 tabs
>71	5 tabs		2 tabs

H – Isoniazid; R – Rifampicin; Z – pyrazinamide; E – Ethambutol

**Table 3: Study drug regimens and duration: Intervention arm**

Pre-treatment body weight	Intensive phase 7 days a week for 8 weeks (56 doses)				Continuation phase – 7 days a week for 16 weeks (112 doses)				
	(kg)	RH (150,75mg)	RH (300,150mg)	Z (500mg)	M (400mg)	RH (150,75mg)	M (400mg)	RH (300,150mg)	M (400mg)
30-37	2 tabs		2 tabs	1 tab	2 tabs	1 tab			
38-54	3 tabs		3 tabs	1 tab	3 tabs	1 tab			
>55		2 tabs	4 tabs	1 tab			2 tabs	1 tab	

H – Isoniazid; R – Rifampicin; Z – pyrazinamide, M - Moxifloxacin

In this study the total duration of TB therapy will be 24 weeks for the intervention arm, and the control arm. The duration of TB treatment may be extended depending on the time to sputum conversion.

In this study the total duration of TB therapy will be 24 weeks for the Intervention arm, and for the Control arm. The duration of TB treatment may increase due to a delay in the time to sputum conversion. This will result in the extension of TB treatment beyond 6 months. The required number of doses must be completed by the patient for the intensive phase of TB treatment before the patient can initiate the continuation phase of TB treatment. The study pharmacist and study clinician will monitor the number of doses ingested, by pill count, for each phase of treatment. The patient’s weight will be assessed monthly and the dose of the study product will be adjusted in accordance with the patient’s weight which will be assessed monthly.

In addition to the 6 months of TB treatment regimen, patients in the Intervention Arm, who provide informed consent to take part in the PK sub-study may be requested to take a single dose of Moxifloxacin 400mg, at the Month 7 visit (or subsequent visit if Month 7 visit has been missed). This PK sample for single dose moxifloxacin may be deferred to month after TB treatment completion on participants who have TB treatment extended beyond 6 months

## 6.2 Study product adverse effect information

Table 4 outlines possible adverse effects and drug interactions. However, this list is not all inclusive and each adverse effect must be examined in conjunction with the full clinical picture. At each clinic visit patients will be asked about adverse events that have occurred since their previous visit and physical examination will be performed.

**Table 4: Possible adverse effects and drug interactions.**

Study Drug	Adverse effects	Drug interactions	Comments
Rifampicin	Gastro-intestinal: nausea, anorexia, mild abdominal pain, diarrhea. Cutaneous reactions: mild flushing and pruritus. Hepatitis especially if alcoholic or history of liver disease.	Efavirenz, nevirapine, protease inhibitors. Rif is an enzyme inducer and increases metabolism of oral anticoagulants (warfarin), oral diabetic drugs, digoxin, phenobarbitone and other anti-epileptics.	Colours urine, sweat and tears orange-pink.

	Serious: flu-like syndrome and shock		
Isoniazid	Peripheral neuropathy, hepatitis (mostly in those > 35yrs), generalized skin rash, fever, joint pains – rare.	Inhibits metabolism of anti-epileptics.	
Ethambutol	Progressive loss of vision caused by retrobulbar neuritis, usually manifests first as loss of colour vision and usually presents after the client has been on treatment for at least two months. This is usually caused by excessive doses of Ethambutol. Skin rash, joint pain, peripheral neuropathy.	There are no known drug–drug interactions involving Ethambutol.	Do not administer if optic neuritis present.
Pyrazinamide	Liver damage: anorexia, mild fever, tender enlargement of the liver and spleen may be followed by jaundice. Arthralgia: This is common and mild. The pain affects both large and small joints, the level of uric acid is increased and gout may occur. Skin rash on sun exposed areas.	Low potential for drug interactions.	
Moxifloxacin	Prolonged QT interval, well tolerated – low rates of gastrointestinal adverse effects.	Potential interaction: Rifampicin, iron/iron containing supplements, aluminium/magnesium containing antacids, zinc/zinc containing supplements, didanosine, sucralfate.	

### 6.3 Pharmacy: Product Supply, Distribution, Accountability and Storage

All TB treatment with the exception of Moxifloxacin will be procured from the Department of Health and where possible fixed dose combinations of drugs will be utilized (outlined in Table 2 and 3). Moxifloxacin 400mg tablets will be procured in bulk quantities from Bayer Healthcare and will be packaged for patient use at the study pharmacy under Good Pharmacy Practice guidance.

The study pharmacy will maintain accountability records of all study products dispensed. In addition, records of manufacturer, batch number and expiry information will be maintained by the study pharmacist. Unused product will be re-issued to the participant at the discretion of the study pharmacist and in accordance with the stipulated dosing schedule.

Dispensing of study product will be done either directly to the study patient or to authorized study staff if the patient is unable to present in person to the study pharmacy.

Study product will be stored between 15- 25°C and temperature records will be maintained at the study pharmacy. Destruction of unused and never dispensed study product will be managed in accordance with the study pharmacy SOP on study product destruction after study PI approval.

#### **6.4 Adherence to study product**

Adherence to study product will be assessed at the study pharmacy at each study visit. This will be achieved by pill count reconciliation and will be documented on a case report form (CRF). Patient self-reported reasons for non-adherence will be assessed and adherence counseling will be provided if needed.

#### **6.5 Antiretroviral treatment and PCP prophylaxis**

Patients, who initiate the study whilst on antiretroviral therapy or during the course of the study require antiretroviral therapy, will be given a regimen that substitutes nevirapine with efavirenz. Patients found to be HIV infected may be given cotrimoxazole/dapsone prophylaxis in accordance with HIV/AIDS guidelines implemented locally.

#### **6.6 Procedure for Urine LAM testing:**

Urine samples will be tested for LAM antigen using the Determine™ TB LAM Ag test (Alere, Waltham, USA). First, participants will be given a urine specimen container and a private space to provide a urine sample. The site nursing staff will use a manufacturer provided pipette to transfer 2 drops (approximately 60 µL) of urine to a small area of the test card. Two people will then independently interpret each result between 25-35 minutes after starting the test. A small reference card, which will aid in correctly interpreting the result, will be available. If positive, the test result will be scored from 1+ to 5+, depending on the severity of the colorimetric line. A score of 1+ represents a weakly positive test result, and a score of 5+ represents a strongly positive test result. Once completed, the test card will be discarded and the urine sample will be placed in frozen storage along with other biologic specimens. The results of the rapid urine test will not be used for clinical treatment decision.

## 7. CLINICAL AND LABORATORY EVALUATIONS

### 7.1 Schedule of Events (SoE)

**Table 5: Study Table of Evaluations**

Procedures	Screening	Baseline	Week			Study Months														
			2	4	6	2	3	4	5	6	7	8	10	12	14-24 (*2 monthly)	End TB Treat	Recurr ence 	Termi nation	Time of IRIS	Time of Serocon version
Inclusion & Exclusion Criteria		X																		
Informed Consent	X																			
Randomization		X																		
HIV test (performed monthly for HIV negative participants)	X 		X			X	X	X	X	X	X	X	X	X	X	X	X	X	X	X
Medical , Medication and TB History & Physical Exam	X	X	X			X	X	X	X	X	X	X	X	X	X	X	X	X	X	X
Vitals (including Pregnancy test )	X	X	X			X	X	X	X	X	X	X	X	X	X	X	X	X	X	X
Contraception confirmation	X	X	X			X	X	X	X	X	X	X	X	X	X	X	X	X		
Concomitant medications	X	X	X			X	X	X	X	X	X	X	X	X		X				
GeneXpert	X																			
Sputum Smear	X	X	X			X	X	X	X	X	X	X	X	X	X	X	X	X		
Culture : INTERVENTION ARM: until 6 months		X	X	X	X	X	X	X	X	X					X	X	X			
Culture: CONTROL ARM: until 6 months		X	X	X	X	X	X	X	X	X					X	X	X			
Susceptibility		X				X				X*		X*				X	X			
PAXgene for SHIP Study		X				X				X		X			X	X	X	X		
Urine (Lam Testing)		X				X			X	X						X				
Chest radiograph		X 					X			X						X	X			
ECG **		X				X		X		X										
Vision testing (Snellen and Ishihara) Control Arm only		X				X														

Procedures	Screening	Baseline	Week			Study Months											End TB Treatment	Recurrence	Termination	Time of IRIS	Time of Seroconversion
			2	4	6	2	3	4	5	6	7	8	10	12	14-24 (*2 monthly)						
AST, ALT, Bilirubin, Hb, platelets, & Full blood count, Creatinine clearance, potassium, total protein, alkaline phosphatase and as clinically indicated	X	X 				X		X		X							X	X	X	X	X
CD4 Count ( HIV Infected patients only )	X					As per SA HIV guidelines														X	
Viral Load ( HIV Infected patients only )	X																	X		X	
HBsAg	X																				
PK Samples (Intervention Arm)				X		X 3				X	X 										
PK Samples (Control Arm)						X															
Specimen Storage		X	X		X		X						X				X				X
PBMCs***		X 				X				X					X	X	X	X	X	X	X

1: HIV Testing is required at screening for all potential participants. Thereafter, HIV testing will be required for HIV negative participants only as per SoE above.

2: A chest radiograph/Bloods will be repeated if they are more than 14 days old

3: PK blood samples, in the intervention arm only, will be taken once during the intensive phase of TB treatment at either Week 4 **OR** Month 2 (**PK bloods may be repeated at Month 2 if these were not taken, incorrectly done or incomplete at Week 4 OR at the discretion of the investigator**), and at the end of TB treatment (Month 6)

4: Additional PK samples will be taken at M7 (or the first visit after if Month 7 is missed) in Intervention Arm before and after the ingestion of the single additional dose of Moxifloxacin. This additional PK sample may be deferred to month after TB treatment completion on participants who have TB treatment extended beyond 6 months

5: If PBMCs are not collected at baseline samples may be taken at Week 4 or Month 2

6. End of TB Treatment visit will be conducted within 7 days of completion of TB treatment.

\* Samples will be collected and stored for future susceptibility testing,

\*\*ECG's will be done at baseline, Month 2 and Month 4 and Month 6. ECG's will be performed 2 monthly during treatment with Moxifloxacin

\*\*\*Additional PBMC's will be collected at IRIS and at the time of seroconversion

The study SoE will be followed except when procedures are clinically indicated as not required.

